8.3.1 By-visit summaries

Overall EDSS score and EDSS functional system scores will be summarized by presenting descriptive statistics for baseline, post-baseline, and change from baseline values by visit. EDSS functional systems are: visual, sensory, brainstem, bowel and bladder, pyramidal, cerebral, and cerebellar.

The number and percentage of patients will be summarized based on EDSS (overall score) change categories: improvement, stable, and deterioration. If baseline EDSS score is ≤ 5 , improvement is indicated by an EDSS score change of ≤ -1 , stable is indicated by an EDSS score change of > -1 and ≤ 0.5 , deterioration is indicated by an EDSS score change of > 0.5 ; if baseline EDSS score is > 5 , improvement is indicated by an EDSS score change of ≤ -0.5 , stable is indicated by an EDSS score change of > -0.5 and ≤ 0 , deterioration is indicated by an EDSS score change of > 0 . Within each visit window, the record with worst category will be selected.

8.3.2 EDSS score of 4/6/7 or greater

The time to first EDSS score of 4/6/7 or greater from first dose of fingolimod among all studies will be analysed for patients with a baseline EDSS score of less than X, where X=4, 6, or 7 depending on the analysis being conducted. Specifically, the number of patients at risk, the cumulative number of patients with event, the Kaplan-Meier (KM) estimate of the percent of patients without event and corresponding standard error and two-sided 95% CI will be provided at each yearly time point (1 year = 360 days).

A Kaplan-Meier plot of 3 Kaplan-Meier curves showing time to first EDSS score of X or greater from first dose of fingolimod to the end of the long-term follow-up study Part will be provided, where X is 4, 6, and 7.

The time to event/censoring for Kaplan-Meier analyses will be calculated as follows:

For patients with EDSS score of 4/6/7 or greater:

Time to event = first assessment date (after first dose date of fingolimod among all studies) that patient has an EDSS score of X or greater – first dose date of fingolimod among all studies +1 day.

For patients who do not have EDSS score of 4/6/7 or greater (in other words, censored):

Time to censoring = last EDSS assessment date – first dose date of fingolimod +1 day. If the patient does not have post-baseline EDSS assessment, then that patient will be censored at Day 1 (Time to censoring =1).

A patient will be censored if the patient exits the study without receiving an EDSS score of 4/6/7 or greater after first dose of fingolimod among all studies.

8.3.3 Analysis of 6-month confirmed disability progression

Disability progression in this study is defined based on an increase in the EDSS score by 1.5 point for patients with a FDF baseline EDSS score of 0, 1 point for patients with FDF baseline EDSS of ≥ 1 and ≤ 5.5 , and by 0.5 points for patients with an FDF baseline EDSS > 5.5 , confirmed after 6 months and all intermediate EDSS assessments. A 6-month confirmed disability progression is defined as a 6-month sustained increase from the reference (potential onset of progression) value in the EDSS scores. i.e., every EDSS score (scheduled or unscheduled) within a 6-month duration after the first progression should

meet the progression criteria as specified above. The confirmation can only happen at a scheduled visit.

To evaluate disability progression, all available scheduled and unscheduled EDSS assessments after the reference time point (e.g. Day 1) will be compared to the EDSS at the reference time point to assess if the change from the reference time point meets the disability progression criteria. The disability progression onset date will be the date of the first EDSS score meeting the disability progression criteria.

The disability progression confirmation can only happen at a scheduled visit and in the absence of a relapse. Note that the end of study or early discontinuation visit and the follow-up visit are protocol specified visits and will be treated as scheduled visits and thus can be used to confirm a disability progression if applicable. Specifically, the confirmation visit for 6-month confirmed disability progression will be the first scheduled visit meeting the following conditions:

- The confirmation visit needs to be ≥ 166 days from the potential onset date and the disability progression criterion needs to be met at that visit (and all visits in between the onset and the confirmation).
- The EDSS is not performed during a relapse (information collected as a flag in the CRF).
- All available EDSS scores (scheduled or unscheduled) between the disability progression onset and this visit meet the disability progression criteria.

If the first scheduled visit after ≥ 166 days for a “6-month confirmed disability progression” does not meet the conditions above, the subsequent scheduled visits will be checked until a confirmation visit is found. If a confirmation visit cannot be found, then above process will be repeated to look for the next disability progression onset and its confirmation visit or until it is certain that no confirmation visit can be found for the progression onset.

A patient is considered to have a 6-month confirmed disability progression if a progression onset with a confirmation visit is found. Otherwise, the patient is considered not to have a 6-month confirmed disability progression and will be referred to as a censored patient.

If a patient died due to MS (EDSS=10), he or she will be considered to have a 6-month confirmed disability progression, irrespective of the EDSS at the reference time point or the change in EDSS.

The time to first 6-month confirmed disability progression from first dose of fingolimod among all studies until the end of the long-term follow-up study part I will be summarized in a yearly interval for fingolimod full analysis set. Specifically, the number of patients at risk, the cumulative number of patients with event, the Kaplan-Meier (KM) estimate of the percent of patients without 6-month confirmed disability progression and corresponding standard error and two-sided 95% CI will be provided at each yearly time point (1 year = 360 days).

A Kaplan-Meier plot of time to first 6-month confirmed disability progression from first dose of fingolimod among all studies to the end of long-term follow-up study part I will be presented.

8.4 Analysis of Multiple Sclerosis Functional Composite (MSFC)

The MSFC assessment is done in patients who had previous assessments during their fingolimod period, including studies CFTY720D2201/E1, CFTY720D2301/E1, CFTY720D2302/E1, CFTY720D2309/E1, and the long-term follow-up study part I. There are 3 components (dimensions) to the MSFC: leg, arm, and cognitive function. The corresponding tests are 25-foot Timed Walking Test (T25FW), 9-Hole Peg Test (9HPT), and Paced Auditory Serial Addition Test 3 (PASAT3). First, the mean score is calculated for each component for each patient at a given time point:

- The average scores of two T25FW trials, i.e.

$$T25FW_{\text{mean}} = \frac{1}{2}(T25FW_1 + T25FW_2)$$

If one of the values is missing, the mean of the remaining values is taken.

- The average scores from the 4 trials on the 9-HPT. For computing 9-HPT subscale, the following will be used:

$$9HPT_{\text{mean}} = \frac{1}{4}(9HPT_{\text{left1}} + 9HPT_{\text{left2}} + 9HPT_{\text{right1}} + 9HPT_{\text{right2}})$$

Mean is only calculated if balanced (i.e., all 4 are available, or 1 from each hand is available).

For the 9-HPT value that will be used in computing the z-score, the mean 9-HPT will be computed differently. The 2 trials for each hand are averaged, converted to the reciprocals of the mean times for each hand and then the 2 reciprocals are averaged, i.e.

$$9HPT_{\text{mean}} = \frac{1}{2} \left(\frac{1}{\frac{1}{2}(9HPT_{\text{left1}} + 9HPT_{\text{left2}})} + \frac{1}{\frac{1}{2}(9HPT_{\text{right1}} + 9HPT_{\text{right2}})} \right)$$

This mean is only calculated if all 4 values are available (ie. none are missing).

- The number of correct answers from the PASAT 3, i.e.

$$PASAT3 = \#correct(PASAT3)$$

Further, a z-score is created for each component. In general, z-scores involve comparing each outcome with that found in a reference population, a process called standardizing each variable. This involves a decision about which population to use as the reference to derive the means and standard deviations to create the z-scores. The preferred method in clinical trials is to use test results from the analysis time-point visit from all patients, with reference population being the baseline population for this study:

- The z-scores for the T25FW

$$T25FW_z = (T25FW_{\text{mean}} - T25FW_{\text{baseline-mean}}) / T25FW_{\text{baseline-stdev}}$$

- The average scores from the 4 trials on the 9-Hole Peg Test (9HPT). The 2 trials for each hand are averaged, converted to the reciprocals of the mean times for each hand and then the 2 reciprocals are averaged, i.e.

$$9HPT_z = (9HPT_{\text{mean}} - 9HPT_{\text{baseline-mean}}) / 9HPT_{\text{baseline-stdev}}$$

- The number of correct answers from the PASAT 3, i.e.

[figure not shown]
$$PASAT3_z = (PASAT3_{\text{mean}} - PASAT3_{\text{baseline-mean}}) / PASAT3_{\text{baseline-stdev}}$$

[figure not shown]
Finally, these individual z-scores are averaged to create an overall composite score:

[figure not shown]
$$MSFC_z = \frac{1}{3} \{9HPT_z - T25FW_z + PASAT3_z\}$$

[figure not shown]
[figure not shown]
The negative value of the T25FT z-score is taken to make the direction of change the same as the other components. In computing $MSFC_z$ for each patient, if any of the individual scores ($9HPT_z$, $T25FW_z$, or $PASAT3_z$) are missing, then $MSFC_z$ will be missing as well.

[figure not shown]
Descriptive statistics on baseline, post-baseline, and change from baseline will be presented for $MSFC_z$ and each subscale score by visit for the fingolimod full analysis set.

9 Safety evaluation

The primary objective of this study is to evaluate the long-term safety and tolerability of fingolimod 0.5 mg in patients with relapsing forms of MS.

Long-term safety will be assessed in terms of adverse events (AEs), laboratory, vital signs (including dose administration monitoring), electrocardiograms (ECG) dose administration monitoring, ophthalmic assessments, pulmonary function tests, and skin assessments. Except for summaries specifically for follow-up (e.g. summaries of Month 3 and Month 6 follow-up visits), serious adverse events, or adverse events after last dose date of fingolimod until end of follow-up, post-baseline safety summaries (not including listings) will limit reporting to only include assessments with dates from first dose date of fingolimod among all studies to last dose date of fingolimod + 45 days.

9.1 Adverse events

9.1.1 Imputation of adverse event start date

Missing or partial adverse event start dates are imputed following the VDW MAP Module 8 ‘Adverse Event Start Date Imputation (#IMPUTAEV)’ section (displayed below):

Adverse Event Start Date Imputation (#IMPUTAEV)

The following table explains the notation used in the logic matrix. Please note that **missing start dates** will not be imputed.

Note, it may happen that the imputed AE start is after AE end date. Missing AE end date is not imputed by STL.

	Day	Month	Year
Partial Adverse Event Start Date	Not used	MON	YYYY
Treatment Start Date (TRTSTD)	Not used	TRTM	TRTY

The following matrix explains the logic behind the imputation.

	MON MISSING	MON < TRTM	MON = TRTM	MON > TRTM
YYYY MISSING	NC	NC	NC	NC
YYYY < TRTY	(D)	(C)	(C)	(C)
YYYY = TRTY	(B)	(C)	(A)	(A)
YYYY > TRTY	(E)	(A)	(A)	(A)

The following table is the legend to the logic matrix.

Relationship	
Before Treatment Start	Partial date indicates AE start date prior to Treatment Start Date
After Treatment Start	Partial date indicates AE start date after Treatment Start Date
Uncertain	Partial date insufficient to determine relationship of AE start date to Treatment Start Date
Imputation Calculation	
NC / Blank Uncertain	No convention
(A) After Treatment Start or Uncertain	MAX(01MONYYYY, TRTSTD+1)
(B) Uncertain	TRTSTD+1
(C) Before Treatment Start	15MONYYYY
(D) Before Treatment Start	01JULYYYY
(E) After Treatment Start	01JANYYYY

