8.1 Analysis of MS Relapses

8.1.1 Relapse date imputations and handling of duplicate relapse records

The start date of a relapse should never be missing. However, missing or partial dates may be expected from some non-phase III trials where data checking may be less vigorous than in phase III trials. To avoid an artificial inflation of the number of relapses by low quality data, missing dates for relapses will only be imputed if the end date of the relapse is after the first dose of the initial study (i.e. if the relapse happened at least partially within the study). If partial or complete end dates are before the first dose date of the initial study, then no imputation will be done. If partial or complete relapse end dates are after the first dose of the initial study, the following algorithm will be applied:

Firstly, drop blanks and impute missing or partially missing start dates

1. Drop complete blanks: If the relapse onset date is invalid (e.g. “No”, “None”) or completely missing and there is no information recorded across all variables, the onset date will be set to missing.
2. Otherwise, if the record is not empty or the onset date is partially missing, check if another record may be available for the same relapse. Concretely:
 - a. If a relapse onset date has a missing day-part (XX-MM-YYYY), where XX represents the missing or invalid part, the onset date will be imputed by the onset date of another treatment-emergent relapse record with a non-missing start date for the same patient within the same month and year, if such a relapse is available (choose the first one if more than one is available).
 - b. If a relapse onset date has a missing day- and month part (XX-XX-YYYY), the onset date will be imputed by the onset date of another treatment-emergent relapse record for the same patient within the same year, if such a relapse is available (choose the first one if more than one is available).
3. Otherwise, if the onset date of a relapse is completely or partially missing, the onset will be imputed with the first possible day within the available non-missing date-part, or the first-dose date, or the relapse end-date minus 90, whatever occurs latest.

Secondly, impute the end date

The imputation of missing or partially missing end dates will be done after the imputation of start dates.

1. If the end date of a relapse is completely missing, it will be imputed as 90 days after the onset date.

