9.1.2.1 Adverse events during long-term follow-up study part I

Adverse events reported during the long-term follow-up study part I will be summarized for the safety set. Unless otherwise specified, all non-serious adverse events recorded in the CFTY720D2399 database with onset on or after first dose date of fingolimod among all studies to last dose date of fingolimod + 45 days are included. All serious adverse events

(SAEs) recorded in the CFTY720D2399 database with onset on or after the first dose date of fingolimod among all studies are also included in the summaries.

Adverse events reported during the long-term follow-up study part I will be summarized by primary system organ class (SOC) and preferred term (PT), and will show the number and percentage of patients with at least one adverse event in each SOC or PT category. Similarly, adverse events by study drug relationship (AEs suspected to be study drug related, AEs not suspected to be study drug related, and AEs regardless of study drug relationship), SAEs, SAEs by study drug relationship, suspected study drug related AEs, and AEs leading to study drug discontinuation will also be summarized by SOC and PT.

AEs and SAEs which are not considered to be known effects of fingolimod treatment (i.e., excluding those listed in the most recent version of Core Data Sheet), will be summarized by PT only.

To determine which AEs occur after discontinuation of fingolimod treatment, all AEs reported with onset date after the last dose of fingolimod until the end of the long-term follow-up study part I will be summarized by SOC and PT for the follow-up set.

Principal cause of death during the long-term follow-up study part I will be summarized by SOC and PT. All deaths recorded in the CFTY720D2399 database with onset on or after the first dose date of fingolimod (among all studies) will be included in the summary.

All information pertaining to any AE with severity information, SAEs, AEs leading to study drug discontinuation, deaths and neoplasms system organ class events that reported during the long-term follow-up study part I will be listed for the safety set. Additionally, adverse events, SAEs and all deaths recorded during the long-term follow-up study part I will be listed for the subgroup of patients from studies D2312 and D2402 in the enrolled set.

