9.1.2.2 Adverse events during the fingolimod treatment period

Unless otherwise specified, all non-serious adverse events with onset on or after first dose date of fingolimod among all studies to last dose date of fingolimod + 45 days are included. All serious adverse events (SAEs) with onset on or after the first dose date of fingolimod among all studies are also included in the summaries. Also, unless otherwise specified, adverse events will be summarized for the fingolimod safety set, by primary system organ class and preferred term, and will show the number of patients with at least one adverse event and the incidence rate of adverse events per 100 patient-years in each SOC or PT category.

The AE incidence rate (IR) is calculated per 100 patient-years. IR is defined as: the number of patients experiencing at least one event in a particular category, over the total patient-years of the “at risk” population for that event multiplied by 100. An underlying Poisson process for incidence rate within treatment group is assumed.

To calculate the total patient-years (time at risk) of the “at risk” population:

1. For patients who have a particular AE category, sum the number of days from first dose date of fingolimod among all studies to the first occurrence of that particular AE category

2. For patients who did not have a particular AE category, sum the number of days from first dose date of fingolimod among all studies to last dose date of fingolimod + 45 days.
3. Add the time at risk for patients who had a particular AE category with the time at risk for patients who did NOT have a particular AE category. This is the total time at risk of that AE category.
4. Divide the total time at risk by 365.25.

Incidence rate of adverse events will be presented for the fingolimod safety set and for the subgroup of fingolimod safety set patients from phase II/III studies, by SOC and PT. Incidence rate of AEs, excluding AE listed in the core data sheet, will be presented by PT. Incidence rate of AEs that fulfill the risk search term (defined in the case retrieval sheet) will be presented by risk name and lower level terms. Similarly, all above indicated AE IR summaries will be conducted for SAEs.

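### The adverse event start-date rule ignores the recorded end date and gives events without a start year no onset, so a few events can be counted on the wrong side of the onset filters

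*SAP*

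**What the plan says.** The text below is in SAP Part I; the Part 2 SAP repeats the imputation rule in its own 9.1.1.

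- **The two sentences on missing dates conflict.** 9.1.1 opens with "Missing or partial adverse event start dates are imputed following the VDW MAP Module 8", then says "Please note that missing start dates will not be imputed". In the matrix, all four cells with the year missing are coded NC. The legend labels that code "NC / Blank Uncertain" and gives no convention for it. The general fallback in 2.4 also leaves a date with no year missing.
- **The end date is not an input.** The matrix uses the month and year of onset and TRTSTD. For a date in the treatment-start month, rule A gives "MAX(01MONYYYY, TRTSTD+1)". For a date with only the treatment-start year, rule B gives TRTSTD+1. The SAP adds "Note, it may happen that the imputed AE start is after AE end date" and offers no correction. TRTSTD is labelled treatment start date but not tied to a particular first dose.
- **Onset decides entry to the tables.** 2.4 says date imputation serves to decide which events enter the summaries. For the fingolimod treatment period, 9.1.2.2 says "All serious adverse events (SAEs) with onset on or after the first dose date of fingolimod among all studies are also included". Non-serious events need onset from first fingolimod dose to last dose + 45 days. The yearly tables need onset inside the interval. The death summary in 9.1.2.1 covers "All deaths recorded in the CFTY720D2399 database with onset on or after the first dose date of fingolimod". The post-discontinuation table needs onset after the last dose.

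**The concern.** There are two separate faults, and they push in opposite directions.

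First, setting an uncertain onset to the day after first dose is a reasonable conservative convention. It stops being reasonable when the recorded end date already shows that the event was over before fingolimod. The D2399 adverse event form accepts events from gaps between studies, including ones already resolved (9.1.2), so pre-drug events can be in the database.

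Second, an event with no start year meets no onset condition, whatever its end date shows. No text says how such an event is to be counted. In the incidence rate, a patient whose only events in a category lack a year is treated as not having had it, and contributes full time at risk to last dose + 45 days.

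Long-term safety is the primary objective. Protocol 1.1 says long-term data are needed to estimate rare or time-dependent events better, and for a rare event one misplaced patient is visible in the rate.

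**Working it through.** The documents give no figure on this point, so there is nothing to reproduce. The check is to apply the matrix as printed, then show how far a rate could move.

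**Step 1: the matrix.** It has 16 cells (year missing, before, same or after, by month missing, before, same or after). Four, all with the year missing, give no date. Two give TRTSTD+1 although true onset may precede the drug: same year with month missing (rule B), and same year and month (rule A).

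**Step 2: worked dates.** Take TRTSTD = first fingolimod dose = 20-Jun-2010, and the filter onset on or after that date.

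| Recorded start | Recorded end | Rule | Imputed start | Passes filter |
|---|---|---|---|---|
| XX-JUN-2010 | 10-Jun-2010 | A | 21-Jun-2010 | yes, though it ended before first dose |
| XX-XX-2010 | 10-Mar-2010 | B | 21-Jun-2010 | yes, though it ended before first dose |
| XX-MAR-2010 | 05-Mar-2010 | C | 15-Mar-2010 | no (start after end, but harmless) |
| XX-XX-2009 | 01-Sep-2009 | D | 01-Jul-2009 | no |
| XX-XX-XXXX | 04-Mar-2012 | NC | none | no, though the end date falls after first dose |

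Capping the imputed start at the end date moves the first two rows before first dose and out of the on-drug tables.

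**Step 3: dependence on TRTSTD.** If TRTSTD is the first core-study dose, rows 1 and 2 apply to patients randomised to fingolimod in the core study. If it is the first D2399 dose, they apply to comparator patients who start fingolimod in D2399. But if it is the first core dose and a comparator patient switches in a later calendar year, an event dated only to the switch year falls under rule E. It is set to 1 January and normally excluded, so the direction reverses.

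**Step 4: illustrative size.** Assumptions: N = 4,150 patients (the enrolment in Amendment 11), F = 5 years each, events at mid-follow-up, and k patients with the event. By the 9.1.2.2 definition,

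IR = 100 × k / [k × F/2 + (N − k) × (F + 45/365.25)].

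- At 1% risk, k = 41.5: 100 × 41.5 / (41.5 × 2.5 + 4,108.5 × 5.1232) = 4,150 / 21,152.4 = 0.196 per 100 patient-years.
- If 10% of those patients have only year-missing events, k = 37.35: 3,735 / (93.4 + 4,112.65 × 5.1232) = 3,735 / 21,163.3 = 0.176, a fall of about 10%. At 1% and 5% the falls are about 1% and 5%.
- If five pre-drug patients are wrongly counted from about day 1: 4,650 / (103.75 + 5/365.25 + 4,103.5 × 5.1232) = 4,650 / 21,126.8 = 0.220, a rise of about 12%. At 5% risk the same five raise the rate from 1.002 to 1.027, about 2.5%.

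**Step 5: records to patients.** The tables count patients with at least one event. If a share q of records lacks a year, independently of patient, someone with m records in the category is lost with probability q^m, which is at most q. So 1% of records gives at most about 1% off the rate of an uncommon event, and less in broad categories where patients have several records.

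**The case against.** The strongest reply is that few events should be affected. Protocol 7.1 requires start and end dates for every adverse event. SAEs are reported within 24 hours (7.2). SAE documentation and the data for primary and safety variables are fully source-verified (8.1), and validation checks and queries follow (8.2, 8.3). An SAE without even a start year should be exceptional. Adverse events, SAEs, deaths and neoplasms reported in the study are listed (SAP 9.1.2.1), with unimputed dates (2.4), so they stay visible. All of this stands and limits the size. It does not correct the tables, from which the rates are reported.

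Protocol 9.4.2 says missing values are not imputed. The SAP nevertheless imputes dates, so the question is only whether its rule uses the information on record.

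Four stronger readings are tempting, and the documents do not support them:

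- *The SAP excludes undated events as policy.* It does not say so. Exclusion follows from a literal reading of the onset filters, and any date with a year is imputed.
- *The primary variable is handled more strictly than secondary ones.* The medication rule in 7.1 also states that missing start dates are not imputed; its contrast is clear only for dates with a month but no year. The relapse rule in 8.1.1 does use the end date, and its last resort is "the onset will be imputed with the first possible day within the available non-missing date-part, or the first-dose date" or the end date minus 90 days, whichever is latest. But it applies only if the relapse ended after the first dose of the initial study, and blank records stay undated.
- *Patients from placebo or interferon gain false on-drug events.* That depends on TRTSTD and can reverse (Step 3).
- *Late-detected malignancies are lost.* Late diagnosis does not imply a missing onset year, and neoplasm events are listed. For a risk with five cases, losing one would cut the count by 1/5 = 20%, but nothing shows that such a case would be undated.

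**Conclusion.** The point holds as a defect in a stated rule that is cheap to repair. As printed, the rule can place an event after its own recorded end and so count a pre-fingolimod event as on-drug. It also leaves year-missing events outside every onset-based table, even when the end date does not rule out on-drug onset.

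The first effect is confined to two matrix cells and requires TRTSTD to be the first fingolimod dose for that patient. The second does not depend on TRTSTD, but it reaches the counts only for patients whose sole event in a category lacks a year.

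The number of such events is not given, and the data checks suggest it is small. A material bias in the primary safety rates is not shown. The percentages in Step 4 rest on assumed follow-up, risk and shares, and show sensitivity only. The two errors have opposite signs but no reason to cancel.

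**What to change.** In 9.1.1 of both SAPs, with matching changes to the table rules in 9.1.2:

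1. Define TRTSTD for this rule as the first fingolimod dose among all studies, and reconcile the two sentences on missing start dates.
2. Cap any imputed start at the recorded end date. Class the event as pre-fingolimod if it ended before the first fingolimod dose.
3. Include a year-missing AE, SAE or death in the overall on-treatment count tables and the all-studies incidence rate. Set onset to first fingolimod dose + 1, or to the start of the study phase in whose database it was first recorded if that is later, but not after the end date. Leave it out if its end date, or the closing date of the database recording it, precedes the first fingolimod dose. For non-serious events, also leave it out if other recorded data place it after last dose + 45 days.
4. Do not assign these events to a yearly interval, and do not count them as new in Part 2 if Part 1 already recorded them. Show them in a separate row for onset unknown.
5. Footnote the number of events affected in each table.

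The cost is a few sentences and a small change to the imputation program. The downside is that a few events of uncertain timing are counted as on-drug, so rates may look slightly less favourable. The footnotes show by how many events.
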